5.4. Per Protocol Set

The Per-Protocol (PP) set will include subjects from mITT set who have no major protocol deviations. Before data are released for statistical analysis, a blinded review of all data will be performed by the Sponsor's clinical team to identify protocol deviations that may potentially affect the results. At this time, it will be determined if subjects and/or data should be excluded from the PP set. The list of subjects or observations to be excluded from the PP set, along with the reason for exclusion, will be finalized prior to database unblinding.

5.5. Pharmacokinetic Set

The Pharmacokinetics (PK) set will include all subjects from safety set who have a valid concentration measurement.

5.6. Protocol Deviations

Protocol deviations will be collected and categorized as shown in the protocol deviation and noncompliance management plan.

6. General Aspects for Statistical Analysis

6.1. General Methods

All analyses and outputs will be produced using SAS[®] version 9.4 or later. Unless otherwise specified, efficacy and safety summaries will be presented for each treatment. All other summaries will be presented for each treatment and overall. Continuous variables will be summarized using the number of observations (n), mean, standard deviation (SD), median, minimum, and maximum. Categorical variables will be summarized using number of observations (n), frequency, and percentages of subjects.

All relevant subject data will be included in listings. All randomized subjects entered into the database will be included in subject data listings. All by visit summaries will use the nominal visit. Unscheduled visits will not be summarized but will be included in the listings.

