^e At Week 4 Study dose should not be taken until after pre-dose blood draw at the site. PK draws should be pre-dose, between 0.5 and 1.5 hours after study drug administration, and between 2 and 4 hours after study drug administration. Both Week 4 and Week 12, visits should be scheduled for the morning. At Week 12, blood sample will be collected in the afternoon at the end of the visit.

^f Study drug will be dispensed for dose down titration.

* Weeks 2 and 10 will be telephone visits. If there are any abnormal findings, the subject will be brought to the site for full assessment. A telephone call will be made to the subject 30 days after the last dose to assess any adverse events that may have occurred.

^g Assessments for these visits may be completed in locations other than study clinic and/or safety and efficacy assessments required at these visits will be made available for remote administration due to restrictions as a consequence of the COVID-19 pandemic or other qualifying event.

^h If visits at Weeks 4 and 12 are completed in locations other than study clinic due to restrictions as a consequence of the COVID-19 pandemic or other qualifying event, then collection of labs for PK assessments are optional

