6.4. Visit Windows

Visit window will not be used in the summarization or analysis of data.

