10.4. Laboratory Evaluations

Blood samples for hematology, biochemistry, and urine samples for urinalysis are to be collected at screening, Baseline, Weeks 12 and 7 day and 14 day Follow Up visits. All results will be provided using International System of Units (SI). HbA1c will be measured at the baseline and completion/early termination visits.

Descriptive statistics for hematology, biochemistry and HbA1c will be provided for each test parameter and for change from baseline treatment by visit and for each treatment group (specific emphasis will be placed on mean changes between ecopipam and placebo in fasting glucose levels and blood lipid parameters). Shift tables (i.e., low-normal-high at Baseline versus low-normal-high at each post-baseline visit in a 3-by-3 contingency table) will be provided for hematology, biochemistry, HbA1c and urine to assess changes from Baseline in laboratory values by visit for each treatment group.

Separate listings will be provided for all laboratory evaluations (hematology, biochemistry, HbA1c and urinalysis.

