10.6. ECG

The following ECG data will be collected at the Screening, Baseline, Week 4, Week 6, Week 8, Week 12, 7 Day Follow Up and 14 day Follow Up visits:

- PR interval (msec)
- QRS interval (msec)
- QT interval

- QTc interval (msec)
- Overall ECG result (Normal; Abnormal, Not Clinically Significant; Abnormal, Clinically Significant).

An ECG is optional at unscheduled visits, per the investigator's discretion.

The actual ECG results along with change from baseline will be summarized at each visit by treatment group. All ECG data will be presented in a listing.

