10.7. Physical Examination

A Physical examination will be performed at the Screening, Baseline, Week 4, Week 6, Week 8, Week 12, 7 Day Follow Up and 14 day Follow Up visits. This will include physical examination of the following body areas and systems: Head, Eyes, Ears, Nose, Mouth, Throat, Neck (including Thyroid); Thorax; Abdomen; Urogenital; Extremities; Neurological; Skin and Mucosae; and Other.

A physical exam is optional at unscheduled visits, per the investigator's discretion.

The Physical examination results will be summarized at each visit by treatment group. All physical examination data will be presented in a listing.

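### Measured safety values from a call-back after an abnormal Week 2 or Week 10 call reach no planned table by arm, and no worst post-baseline summary picks them up

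*SAP*

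**What the plan says.** SAP 6.1 sets two rules for every by-visit output: "All by visit summaries will use the nominal visit", and "Unscheduled visits will not be summarized but will be included in the listings". Neither carries an exception for safety. SAP 6.4 adds that "Visit window will not be used in the summarization or analysis of data", so an off-schedule value is not mapped back to a planned visit.

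The Schedule of Assessments (Protocol Table 2, in Section 7.5, and SAP 14.1) makes Weeks 2 and 10 telephone visits. Its footnote says of those calls: "If there are any abnormal findings, the subject will be brought to the site for full assessment". The contents of that assessment are not defined, and neither document says under which visit it is recorded.

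The safety outputs in SAP Section 10 are tied to planned visits. Lab shift tables compare "low-normal-high at Baseline versus low-normal-high at each post-baseline visit in a 3-by-3 contingency table". Vital signs are summarized at scheduled time points (10.5), and ECG and physical examination by visit (10.6, 10.7). The C-SSRS and the other scales are summarized at Baseline and Weeks 4, 6, 8 and 12 (10.8, 10.9).

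SAP 10.6 says "An ECG is optional at unscheduled visits, per the investigator's discretion", and SAP 10.7 says "A physical exam is optional at unscheduled visits, per the investigator's discretion".

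**The concern.** A call-back visit happens because something on the telephone looked abnormal. If its measurements appear only in listings, a reader comparing arms on labs, ECG, blood pressure or mood and movement scales does not see them.

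Safety is a secondary objective, and the background gives reasons to look closely. Protocol 5.2.2.1 reports that the Phase 3 obesity studies were stopped for psychiatric events (31% on ecopipam against 15% on placebo). Protocol 5.3.1 says that orthostatic blood pressure data were lacking from earlier work. SAP 10.4 itself singles out fasting glucose and lipids for attention. The first of the two call-only intervals, Baseline to Week 4, covers the whole up-titration.

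**Working it through.** The plan gives no figure on this point, so the check sets the schedule beside each planned output.

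**1. On-treatment contacts.** Protocol 5.3.3 counts 4 site evaluations and 2 telephone evaluations. By Table 2 the site visits are Weeks 4, 6, 8 and 12, and the calls are Weeks 2 and 10. So 2 of 6 contacts have no planned on-site measurement. The two intervals whose only contact is a call are Baseline to Week 4 and Week 8 to Week 12, which is 4 + 4 = 8 of the 12 weeks.

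**2. Time from a call to the next summarized value, for a subject who stays on schedule.**

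| Measure | Planned on-treatment points after Baseline | After a Week 2 call | After a Week 10 call |
|---|---|---|---|
| Labs (SAP 10.4) | Week 12 or early termination | 12 − 2 = 10 weeks | 12 − 10 = 2 weeks |
| Vital signs, ECG, physical exam (10.5–10.7) | Weeks 4, 6, 8, 12 | 4 − 2 = 2 weeks | 2 weeks |
| AIMS, BARS, SNAP-IV, CY-BOCS, CDRS-R, PARS (10.9) | Weeks 4, 6, 8, 12 | 2 weeks | 2 weeks |

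An abnormality that resolves inside the gap leaves no trace in the arm-level tables of measured values.

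**3. Does the label on the call-back change this?**
- Recorded as unscheduled: SAP 6.1 keeps it out of the summaries.
- Recorded under the call's own number (Visit 3 or 7): SAP 6.1 does not exclude it, but no output plans for it. The collection visits listed for labs and ECG omit Weeks 2 and 10, vital signs have no scheduled measurement there, and the scales are summarized at named weeks that omit both.

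Under either label, no planned table receives the values.

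**4. Is there a worst-value table elsewhere?** SAP Section 10 has none for labs, ECG, blood pressure or scales. The nearest outputs are adverse events by highest CTCAE grade and by maximum severity (10.3), which grade events, and weight gain of at least 7% (10.5), for which no time point is given.

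**5. C-SSRS.** It is scheduled at eight post-baseline visits: Weeks 2, 4, 6, 8, 10 and 12 and the 7- and 14-day follow-ups. SAP 10.8 summarizes four (Weeks 4, 6, 8 and 12). The Week 2 and Week 10 results are planned data, so their omission does not depend on how a call-back is labelled.

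**6. What the adverse event tables still capture.** The TEAE, SAE, AESI and discontinuation tables count subjects with an event, whichever visit revealed it. Protocol 12.2.1 gives four routes by which an abnormal test becomes an adverse event: it causes signs or symptoms, needs active intervention, needs study drug interrupted or stopped, or is judged clinically significant. Protocol 12.4 makes recording compulsory when a value constitutes an SAE or leads to stopping study drug. It leaves other clinically significant lab, blood pressure and pulse changes to the investigator. An event record also does not put the measured value in a table.

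**The case against.** The strongest reply is that important findings are not lost. A symptomatic, treated or drug-stopping abnormality meets an adverse event criterion whether or not anyone judges the value clinically significant, and Protocol 12.1.3 requires signs of abuse, withdrawal or dependence to be recorded as adverse events. This stands. A reader might infer from SAP 6.1 that call-back findings appear in listings only. The documents do not support that, because the adverse event tables are not tied to visits. What remains is the abnormal value that meets no criterion or is not reported, and the measured value in every case.

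A second reply is that leaving symptom-triggered measurements out of by-visit means is sound practice, since such measurements may be taken unequally between arms. This also stands, and those means should not change. It does not explain why no supplementary any-time table is planned. A reader might further infer that the tables are biased toward no difference. That direction is plausible but not shown: no document gives a rate of abnormal calls in either arm.

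Third, the schedule footnote never calls the call-back unscheduled, and Weeks 2 and 10 are numbered visits. Treating it as unscheduled is an inference. The conclusion does not need it, because neither label leads to a planned table.

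Two other readings should be set aside. The Week 4 window opens at Day 25, but that date excludes nothing: analysis is by nominal visit without windows, so an early Week 4 visit is still summarized as Week 4. Early-termination assessments are not at issue either, since they share a scheduled column with Week 12.

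**Conclusion.** The point holds for measured safety values. Lab, vital-sign, ECG and scale results from a call-back after a Week 2 or Week 10 call reach no planned table by arm, and no worst post-baseline or any-time table makes up for it. The adverse event tables are a partial substitute. The gap is about 10 weeks for labs after a Week 2 call and about 2 weeks for the other cases. Separately, the scheduled Week 2 and Week 10 C-SSRS results are missing from the SAP 10.8 summary.

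This assumes that the call-back assessment includes some of these measurements, which the footnote implies without listing them. The number of subjects affected and the effect on any arm comparison cannot be stated from the documents. This is an inexpensive improvement to descriptive safety reporting and has no bearing on the efficacy analysis.

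**What to change.** Keep the by-visit descriptive tables on scheduled visits. Add to SAP 6.1 and Section 10 that each subject's worst post-baseline value, taken from all scheduled and unscheduled visits, is used by arm for:

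- baseline-to-worst lab shift tables, with shifts to low and to high shown separately;
- ECG and blood pressure outlier counts, with cut-offs fixed before unblinding;
- maximum CDRS-R, PARS and BARS scores.

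Add to SAP 10.8 a summary of any-time post-baseline C-SSRS ideation and behavior that includes the telephone visits.

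State whether a call-back is recorded under Visit 3 or 7 or as unscheduled. Reconcile the footnote's full assessment with SAP 10.6 and 10.7, which leave ECG and physical examination optional at unscheduled visits.

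The cost is SAP wording and a few extra tables from data already collected, with no new procedure. The drawback is that symptom-triggered measurements may be more frequent in one arm, so the worst-value tables should be read beside the by-visit ones.

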6.2. Key Definitions

Treatment emergent adverse events (TEAEs) are defined as any adverse events that start or increase in intensity on or after the first dose of Double-blind treatment on Day 1.

Timing specific adverse events are defined as any adverse events that occur or increase in intensity during any specifically defined study milestones: treatment phase (TPAE), taper down (TDAE) and off study drug (ODAE).

Duration of exposure is defined as (Date of Last Dose – Date of First Dose) +1. If date of last dose is unknown then the date of last clinical visit will be used to impute the date of last dose.

Baseline is defined as the last measurement taken before the first dose of double-blind treatment on Day 1.

6.3. Missing Data

Partial dates of medications will be imputed solely for the purpose of defining prior/concomitant status for medications. Dates will be defined using the hierarchy of derivations below.

- For missing start day where month and year are present, the start day will be set to the 1st of the
 month, unless the month and year are the same as the first dose month and year and the 1st of
 the month is before the first dose date, in which case, the start date will be set to the first dose date.
- For missing start day and month where year is present, the start day and month will be set to January 1st, unless the year is the same as the first dose year and January 1st is before the first dose date, in which case, the start date will be set to the first dose date.
- For missing end day where month and year are present, the end day will be set to the last day of the month, unless the month and year are the same as the trial termination month and year, in which case, the end date will be set to the trial termination date.
- For missing end day and month, where year is present, the end date will be set to the trial termination date if the years are the same. If the trial termination year is greater than the end year, the end day and month will be set to December 31st.

Partial onset dates for adverse events will be imputed in the same manner described above for partial start dates for the purpose of defining treatment emergent status.

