12.4. Recording Adverse Events

Adverse events spontaneously reported by the subject and/or in response to an open question from the study personnel or revealed by observation will be recorded during the study at the investigational site. Clinically significant changes in laboratory values, blood pressure, and pulse can be reported as AEs per the investigator's judgement. However, abnormal values that constitute an SAE or lead to discontinuation of administration of study drug must be reported and recorded as an AE. Information about AEs will be collected from the signing of consent form until the end of the study. SAE information will be collected from signing of consent form until 30 days following the last dose of study drug. The AE term should be reported in standard medical terminology when possible. For each AE, the investigator will evaluate and report the onset (date and time), resolution (date and time), intensity, causality, action taken, serious outcome (if applicable), and whether or not it caused the subject to discontinue the study.

Intensity will be assessed according to the following scale:

- Mild (awareness of sign or symptom, but easily tolerated)
- Moderate (discomfort sufficient to cause interference with normal activities)

• Severe (incapacitating, with inability to perform normal activities)

It is important to distinguish between serious and severe AEs. Severity is a measure of intensity whereas seriousness is defined by the criteria under Section 12.2.1.2. An AE of severe intensity may not be considered serious.

Should a pregnancy of a subject or partner occur, it must be reported and recorded on Sponsor's or Sponsor approved pregnancy form. Pregnancy in itself is not regarded as an AE unless there is a suspicion that an investigational product may have interfered with the effectiveness of a contraceptive medication. Reports of pregnancy must be submitted to Syneos Health Safety & Pharmacovigilance within one business day:

Email Address: [contact] Fax no. Americas: [contact] Fax no. Europe and ROW [name]

The outcome of all pregnancies (spontaneous miscarriage, elective termination, normal birth or congenital abnormality) must be followed up and documented even if the subject was discontinued from the study.

All reports of congenital abnormalities/birth defects are SAEs. Spontaneous miscarriages should also be reported and handled as SAEs. Elective abortions without complications should not be handled as AEs.

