7.4.2. Concomitant Medication

Concomitant medications are defined as medication on the eCRF that are taken on or after or are ongoing at the start date of dosing. Concomitant medications will be summarized by ATC level 2 and preferred drug name for the Safety Set.

8. Efficacy

The mITT set will be used for the analysis of the efficacy endpoints.

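### The partial-date rule in SAP 6.3 ignores a recorded end date, so an adverse event that resolved before dosing can be counted as treatment-emergent

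*SAP*

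**What the plan says.** SAP 6.3 has two start-date rules. With the day missing, the start defaults to the 1st of the month. With day and month missing, it defaults to January 1st. Each has an exception. The day-missing rule departs from its default when month and year equal those of the first dose and the 1st precedes dosing. The year-only rule applies its default "unless the year is the same as the first dose year and January 1st is before the first dose date". In both exceptions the outcome is the same: "in which case, the start date will be set to the first dose date".

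The section then extends this to safety data: "Partial onset dates for adverse events will be imputed in the same manner described above for partial start dates", in order to set treatment-emergent status. SAP 6.2 defines TEAEs as "adverse events that start or increase in intensity on or after the first dose of Double-blind treatment on Day 1". The definition depends on start or worsening; the stop date plays no part. SAP 10 and 10.3 restate the TEAE definition without adding a stop-date condition.

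Protocol 12.4 starts collection before dosing: "Information about AEs will be collected from the signing of consent form until the end of the study". Screening can last up to 28 days (SAP 3.3).

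For medications, SAP 7.4.1 classes a drug as prior if it either started or ended before the first dose. SAP 7.4.2 classes it as concomitant if it is "taken on or after or are ongoing at the start date of dosing".

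**The concern.** Moving an ambiguous onset to Day 1 is a sensible conservative convention when the event could have begun on treatment. It is not conservative when a recorded stop date before the first dose proves that it did not. In that case the rule overrides collected data, creates a record whose start follows its end, and puts a resolved screening event into the TEAE tables.

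Such events are foreseeable, because AEs are recorded at Screening and Baseline. At stake is the accuracy of the TEAE counts and, to a lesser degree, of the prior-medication table. If the rule is left as it stands, records with a start after their end will probably be queried during programming and settled case by case. It is better to settle them in advance.

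**Working it through.** The plan states no figure to reproduce here. The check applies the two SAP 6.3 rules literally, first to single records and then to an enumeration.

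**Single records, first dose 20 Nov 2020**

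| Record | Known start | Recorded end | Imputed start | Result |
|---|---|---|---|---|
| AE, day missing | Nov 2020 | 9 Nov 2020 | 20 Nov 2020 | Start after end; TEAE |
| AE, day missing | Oct 2020 | 9 Nov 2020 | 1 Oct 2020 | Not a TEAE (correct) |
| Drug, year only | 2020 | 31 May 2020 | 20 Nov 2020 | Start after end; prior by its end date (7.4.1) |
| Drug, year only | 2019 | 31 May 2020 | 1 Jan 2019 | Prior (correct) |
| Drug, year only | 2020 | ongoing | 20 Nov 2020 | Neither starts nor ends before dosing: not prior; concomitant |

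The rule fires only when the known part matches the first dose. The last row matters because Protocol 8.2, criterion 19, admits antidepressant, anti-anxiety and ADHD drugs only at a dose already stable for at least 4 weeks before Screening. Such a drug was certainly taken before dosing, yet it leaves the prior table. It is correctly concomitant either way.

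**Enumeration for AEs**

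Inputs: 730 first-dose dates (every day from 1 Jan 2020 to 30 Dec 2021); true onset 1 to 28 days before dosing, equally likely (28 days is the screening maximum); duration d = 1, 3 or 7 days (assumed); only events that ended before dosing are kept. An onset b days before dosing qualifies when b ≥ d, so each first-dose date contributes 29 − d events:

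- d = 1: 730 × 28 = 20,440
- d = 3: 730 × 26 = 18,980
- d = 7: 730 × 22 = 16,060

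| Duration | Day missing: counted as TEAE | Day and month missing: counted as TEAE |
|---|---|---|
| 1 day | 10,696 / 20,440 = 52.3% | 19,628 / 20,440 = 96.0% |
| 3 days | 9,308 / 18,980 = 49.0% | 18,174 / 18,980 = 95.8% |
| 7 days | 6,820 / 16,060 = 42.5% | 15,290 / 16,060 = 95.2% |

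**Hand check of the first row**

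- *Day missing.* A first dose on day D of a month has min(D − 1, 28) qualifying onsets in that month. Summed over D, this gives 462 for a 31-day month, 434 for 30 days, 406 for 29 and 378 for 28. For 2020: 7 × 462 + 4 × 434 + 406 = 5,376. For 2021: 7 × 462 + 4 × 434 + 378 = 5,348. Leaving out 31 Dec 2021 removes 28: 5,376 + 5,348 − 28 = 10,696.
- *Day and month missing.* The only events that escape have an onset in the previous calendar year: 28 + 27 + … + 1 = 406 per year. 20,440 − 2 × 406 = 19,628.

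With exponential durations of mean 2, 4 and 7 days in place of fixed ones, a simulation of 200,000 draws gives 50%, 48% and 45% for the day-missing case.

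**With the guard.** If an imputed start may not exceed the recorded end, the number misclassified is 0 in all six cells.

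**The case against.** The strongest reply is that few records qualify. Protocol 12.4 asks the investigator for the date and time of both onset and resolution of every AE, and a screening event arises within about four weeks of clinic contact. A record must lack its onset day yet carry a stop date. That stands: the percentages above are shares of this subgroup, not of all AEs, and no count of miscoded TEAEs can be given. The year-only case should be rarer still for AEs.

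It is also fair that the rule errs toward counting events as treatment-emergent, that it is identical in both arms, and that all data are listed.

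A reader might infer more than the documents support:

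- *Washed-out tic drugs become concomitant.* A drug with a recorded pre-dose end is prior under SAP 7.4.1, and it is neither taken on or after dosing nor ongoing, as SAP 7.4.2 requires. It would be called concomitant only if a program read status from the imputed start and ignored the recorded stop, which the definitions do not call for.
- *The estimand or per-protocol set is affected.* SAP 4.1.1 handles prohibited medication by treatment policy, so observed Week 12 data are used whatever the flag. Per-protocol exclusions come from a blinded review of the data (SAP 5.4), not from an imputed flag.
- *A stable drug is reported as newly started on Day 1.* SAP 6.3 limits medication-date imputation to prior/concomitant status, and the medication tables are by ATC class and drug name, not start date.
- *The drug-placebo contrast is materially diluted.* If a fraction q of each arm gains a false TEAE independently of true incidences p₁ and p₀, the difference becomes (1 − q)(p₁ − p₀). With q small this is nearly unchanged; only ratios move toward 1 more noticeably.

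**Conclusion.** The point holds in a narrow form. As written, SAP 6.3 gives a provably wrong classification to an AE with a partial onset that matches the first-dose month and year (or year alone) and a recorded stop before dosing. Among pre-dose AEs that resolved before dosing and have a partial onset, roughly 42-52% (day missing) or about 95% (day and month missing) would be called treatment-emergent. These shares rest on uniform onset over 28 days and durations of 1 to 7 days. The number of partial dates is not in the documents and is probably small.

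The consequence is a modest inflation of TEAE counts in both arms, with no effect on the primary efficacy analysis. For medications, the loss that follows from the text is of ongoing drugs, already taken before dosing, whose only known start date is the dosing year: they go missing from the prior table. This is a minor correction, worth making because it is cheap and unambiguous.

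**What to change.** Add to SAP 6.3:

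> An imputed start date may not be later than a recorded end date; an AE or medication with a recorded end date before first dose is not treatment-emergent or concomitant. A medication recorded at Screening or Baseline as already being taken is treated as started before first dose.

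Keep the move to the first-dose date for all other partial dates, that is, where the end date is on or after first dose, ongoing or unknown.

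The cost is two sentences of SAP text and the matching conditions in the date-imputation program. No new data are needed: medication history and concomitant medications are already scheduled at Screening and Baseline. The change should be made before unblinding.
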